#### **6.2 Secondary Endpoints**

Secondary endpoints will be the difference in StimQ scores, and the information about reading practices and activities from the ERPO, collected approximately 1 month after the infant has, or is age-eligible for, their 6, 9, and 12 month well visits for the randomized control trial, the DialogPR-I collected between 9 and 18 months, 30 days, as well as themes derived from the transcripts of the video and audio-recordings in the Video Sub-study. The Video Sub-study is contributing to the main study's exploration of dialogic reading behaviors when comparing e-

books to standard board books, and determining the comparative effectiveness of digital literacy promotion to standard literacy promotion on parent-child language interaction and parent reading behaviors.

### 6.3 Statistical Methods

Summary statistics will be obtained, and differences between digital and standard arms will be assessed using intention-to-treat analysis. Cross-sectional differences in StimQ scores between digital and standard groups at the 6, 9 and 12 month well visits will be assessed using t-tests. To determine how the effects of digital versus standard literacy is associated with language development, we will develop regression models using longitudinal data methods that adjust for correlation in BSID-III scores over time and for potential confounding by demographic characteristics. To explore the impact of digital literacy on healthcare utilization, the EHR will be reviewed to identify a subjects' number of well visits and their vaccination history.

To determine whether parent adversity, health literacy, and/or parent mental health modify the effects of digital versus standard literacy on language development, we will develop similar regression models using longitudinal data methods, but we will also fit interaction terms between study group and ACE score ( $\geq 4$ ), SAHL (high or low) and EPDS score ( $> 10$ ). To determine if parent-child reading activity mediates the association of intervention group assignment and language development, we will use mediation analysis with separate models regressing group assignment on language development, parent-child reading activity on group assignment, and group assignment on language development adjusted for parent-child reading activity.

Assuming a mean cognitive subscale on the BSID-III of 96, a power of 0.70, an alpha of 0.05, and a clinically significant difference of 7.5 points on the BSID-III between groups, we estimate that we will need to recruit a total sample size of 100 eligible children (50 in each group) to participate in the main RCT study (Figure 1). To attain thematic saturation in the Video Sub-study, we will recruit up to 40 participants 9-12 months of age. These 40 participants may be recruited external to the main study if we are unable to recruit up to 40 from the 100 enrolled in the main study in a timely fashion. All analyses will be conducted using Stata Statistical Software, version 13 (College Station, TX).

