Participants in both study arms will be followed every 3 to 4 months until the infants are between the ages of 12 and 18 months, 30 days. Information on reading activities and developmental outcomes will be collected in concert with scheduled well child visits. Differences in reading activities and developmental outcomes will be assessed between groups using intention-to-treat analysis. Parents will complete measures of demographics, health literacy, and maternal depressive symptoms at baseline. Parents will also complete measures of reading activity with their infant about 1 month after the child has, or is age-eligible for, their 6, 9, and 12 month well visits. The infant will also receive a developmental assessment at the second study visit which will happen about 1 month after they have, or are age-eligible for, their 12 month well visit. At this time the infant should be between 12 and 18 months, 30 days old. Secondary data to address these study questions does not exist, which will necessitate the collection of new data as proposed here. We anticipate that this collection of rich new data will support a careful assessment of the effects of digital vs. standard literacy promotion. The HER will be reviewed for children in both arms to count the number of well child visits and examine their vaccination history.

We anticipate collecting this data in conjunction with well child visits. In our experience, low-income families can be difficult to reach for study visits, even with appropriate study incentives. By coordinating data collection with the 6, 9, and 12 month well child visits timeframes, we can increase the probability of families attending both the well visits (to receive the Reach Out and Read Program materials) and the study visits (to collect measures of reading activity and development). In a previous study of 2100 children enrolled in a study of developmental screening, we were able to achieve a >90% follow-up rate by coordinating data collection with well child visits. In addition, our research staff can check the clinic schedule to ensure families have made timely well child visit appointments and then make reminder calls to families prior to these visits to encourage parents to attend. Study visits will be held at a location that is preferred

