Written informed consent will be obtained in person prior to any study related procedures being performed. The consenting process will include a discussion of study rationale, procedures, measures, benefits, risks, and alternatives to participation. After consent, subjects will either be assigned to the digital literacy arm or the standard literacy arm of the study. Regardless of their assignment, once they have consented to participate, they will complete a demographic questionnaire (Appendix 1), questionnaires about adverse childhood experiences (Appendix 2) and health literacy (Appendix 3), and the Edinburgh Postnatal Depression Scale (EPDS) (Appendix 4).

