## **4 STUDY PROCEDURES**

### **4.1 Screening/Consenting Visit and Study Visit 1**

- Identify eligible 4-month old infants at the time of their well child visit using the electronic health record (EHR)
- Recruit and consent eligible parent-child dyads at or before child's 6 month well visit.
- Randomize parent-child dyads into intervention and control groups.
- Collect baseline demographic, parent adversity, and parent mental health information.

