## 4.2 Study Treatment Phase

- Implement an EHR alert to remind clinicians which arm (digital or standard) the patients are in at time of well visits at 6, 9 and 12 months.
- Provide developmentally appropriate standard books or e-books and a bookmark to clinicians to give to participants at 6, 9, and 12 month well visits.
- Parents will complete measures of reading activity (StimQ and ERPQ) via REDCap survey sent to their email about 1 month subsequent to the time the child has, or is age-eligible for, their 6 and 9 month well visits.
- Phone calls and/or text messages will be made to all participants throughout the study to remind them to schedule and/or attend well visit, and for other study-related reminders.
- Selected parents will complete a videotaped reading task at a scheduled time convenient to the participant and after the participant becomes age-eligible for their 9 month well visit. For parents enrolled external to the larger randomized control trial, this will be the only study visit completed by these participants. These participants will complete the study related questionnaires, including the demographic questionnaire, the ACE, SAHL, EPDS, StimQ and ERPQ, at the time of this study visit. Participants enrolled in the sub-study (either within the RCT or externally) will additionally complete the paper-based DialogPR-I at the time of their video sub-study visit.
- Contact participant after the child has, or is age-eligible for, the 12 month well visit to schedule the second study visit.
- At the second study visit, about 1 month after the child has, or is age-eligible for, the 12 month well visit, parents will complete measures of reading activity (StimQ, ERPQ and DialogPR-I) in addition to a measure concerning depressive symptoms (EPDS), and their child will receive a developmental assessment (BSID-III) administered by the study's Early Childhood Assessor.

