### **6 STATISTICAL CONSIDERATIONS**

#### **6.1 Primary Endpoint**

The primary endpoint for the randomized control trial will be the BSID-III scores at the second study visit when the child is between 12 and 18 months, 30 days of age.

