### **7.2 Adverse Event Reporting**

Since the study procedures are not greater than minimal risk, SAEs are not expected. If any unanticipated problems related to the research involving risks to subjects or others happen during the course of this study (including SAEs) they will be reported to the IRB in accordance with CHOP IRB SOP 408: Unanticipated Problems Involving Risks to Subjects. AEs that are not serious but that are notable and could involve risks to subjects will be summarized in narrative or other format and submitted to the IRB at the time of continuing review. We will query participants concerning any disclosures of PHI at each study visit. We will only query participants once concerning childhood trauma at the baseline visit and twice concerning depressive symptoms at the baseline and second (final) study visit.

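### Section 6.3 plans longitudinal models for BSID-III, but each child has one BSID-III assessment; specify a single-time regression on one named scale

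*Combined protocol and SAP*

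**What the plan says.** Section 6.1 sets a single time for the outcome: "The primary endpoint for the randomized control trial will be the BSID-III scores at the second study visit", at an age between 12 months and 18 months 30 days. Section 3.1.1 agrees ("The infant will also receive a developmental assessment at the second study visit"), and section 4.2 lists the BSID-III among the procedures of that visit only. Sections 7.2 and 8.6.1 call the second visit final; section 7.2, for example, has parents questioned "twice concerning depressive symptoms at the baseline and second (final) study visit".

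At study visit 1 the plan asks for other things. Section 4.1 reads "Collect baseline demographic, parent adversity, and parent mental health information", and section 3.1.3.1 lists the demographic, adversity, health literacy and depression questionnaires. Neither mentions the BSID-III.

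Section 6.3 nevertheless describes the language-development analysis as "regression models using longitudinal data methods that adjust for correlation in BSID-III scores over time", with further adjustment for demographic characteristics. For effect modification it adds: "we will develop similar regression models using longitudinal data methods, but we will also fit interaction terms between study group" and ACE, SAHL and EPDS categories. StimQ, which is collected three times after enrolment for the secondary endpoint (section 6.2), is given cross-sectional t-tests.

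**The concern.** The model described for the primary outcome is for repeated scores, which the trial does not collect. An analyst cannot follow the text literally and would have to decide, without guidance from the plan, what to fit instead. The same wording carries over to the three interaction analyses.

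The gap is wider because the outcome variable is also open. Section 5.1.6 describes an instrument with cognitive, language and motor parts. The primary objective (section 2.1) and the models in section 6.3 refer to language, section 6.1 refers to scores without naming a scale, and the sample-size statement uses the cognitive subscale. Both the model form and the scale could therefore be settled after data are available.

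**Working it through.** **1. Count the BSID-III assessments per child.**

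| Contact | Instruments listed | BSID-III |
|---|---|---|
| Study visit 1 (3.1.3.1, 4.1) | Demographics, ACE, SAHL, EPDS; 3.1.4 adds reading activity | 0 |
| About 1 month after the 6-month well visit (4.2) | StimQ, ERPQ | 0 |
| About 1 month after the 9-month well visit (4.2) | StimQ, ERPQ | 0 |
| Second, final study visit (4.2, 6.1) | StimQ, ERPQ, DialogPR-I, EPDS, BSID-III | 1 |

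The total is one. The Abstract gives the same schedule.

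**2. Reproduce the plan's sample size.** The inputs are a difference of 7.5 points, alpha 0.05 and power 0.70 (section 6.3), and SD 15 (Figure 1). Sidedness is not stated, so two-sided is assumed.

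n per arm = 2 × (z for alpha/2 + z for power)² × SD² / difference², and SD²/difference² = 225/56.25 = 4.

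- Power 0.60: 8 × (1.960 + 0.253)² = 39.2, so 40 per arm, 80 in total.
- Power 0.65: 8 × (1.95996 + 0.38532)² = 44.003, so 45 per arm, 90 in total.
- Power 0.70: 8 × (1.960 + 0.524)² = 49.4, so 50 per arm, 100 in total.

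All three rows of Figure 1 are matched. One-sided testing would give 58, 66 and 76, so two-sided is the reading that fits. Power from the noncentral t distribution at 40, 45 and 50 per arm is 0.598, 0.650 and 0.697. The formula has no number of time points and no within-child correlation: it is already a comparison of one score per child.

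**3. What a longitudinal model does with one score per child.** In a random-intercept model the variance of a child's score is between-child variance plus residual variance. With one score, the likelihood depends only on that sum. At SD 15 the sum is 225 however it is split. The standard error of the arm difference is √(225 × (1/50 + 1/50)) = √9 = 3.0 points for every split, the same as in ordinary regression. In one simulated data set of 100 children with total variance fixed at 225, the log-likelihood was −398.886 at within-child correlations of 0, 0.25, 0.5, 0.75 and 1. The data carry no information about that correlation.

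An exchangeable GEE gave the ordinary-regression arm estimate, with a standard error 0.990 of the ordinary one. That matches √(49/50) = 0.990, the small-sample difference between the robust and the pooled formula.

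**4. Effect of the corrected model on size and power.** With the same inputs and covariates that explain no variance, the sample size stays at 100 and power at 0.697 (t) or 0.705 (normal approximation).

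**5. Scale.** The plan does not say that several scales would be tested. As an illustration only, testing two scales at 0.05 each and counting either gives a false-positive chance of 1 − 0.95² = 0.0975 if they are independent. Three scales give 1 − 0.95³ = 0.143. Positive correlation between scales would lower both figures.

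**The case against.** The best defence is that nothing goes wrong numerically: a competent analyst would see one row per child, fit ordinary regression, and obtain the result that the sample size was built for. That stands, and it limits the weight of the point.

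A second defence is that section 3.1.1 ties developmental outcomes to scheduled well child visits and has follow-up every 3 to 4 months, which could suggest repeated testing. It does not hold, because the same section then places the assessment at the second visit, as do the Abstract and sections 4.2 and 6.1. Nor do several BSID-III scales per child rescue the wording: they are correlated across domains, not over time.

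A third is that section 6.3 contains other analyses. This is correct. The mediation models also relate arm to language development, without longitudinal wording, and section 6.3 promises intention-to-treat comparisons between arms in general terms. A reader might infer that the plan has no other regression involving BSID-III, and that would be too strong. The mediation models serve a different question, however, and the general statement names no test. The longitudinal model is the only regression planned specifically for the treatment comparison on BSID-III.

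A reader might also infer that a random-intercept fit would give a standard error that is too small and raise the false-positive rate. The documents do not support this. The standard error depends on total variance, which is identified (step 3). A wrong value would come from software failing on an unidentified split of the variance, and it is not a property of the model. The plan names Stata 13, which was not tested.

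**Conclusion.** The contradiction is real and should be corrected: section 6.3 adjusts for a correlation over time that one BSID-III score per child cannot contain, in both the treatment-comparison model and the interaction models. The direct numerical effect is about nil. The sample size of 100 and power of about 0.70 stand, given two-sided testing, SD 15 and a 7.5-point difference. It would be wrong to infer from this point that the trial is mis-sized or its error rate inflated.

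The consequence is one of specification. The model and the scale for the primary comparison are not fixed in a form that can be followed. The conclusion rests on the schedule as written, which is consistent everywhere that the BSID-III is placed. No gain in power from site adjustment is claimed, because the documents give neither site sizes nor the variance that site explains.

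**What to change.** - In section 6.3, replace the longitudinal wording for BSID-III with one linear regression of the second-visit score on arm, clinic site and baseline demographic covariates named in advance. Site is the randomisation stratum (section 3.2); including it follows the design and is not the correction of a bias.
- For ACE, SAHL and EPDS, use the same model plus the modifier's main effect and its arm-by-modifier term.
- In section 6.1, name one BSID-III scale as primary, and make the objective, the models and the sample-size sentence refer to it. The choice is the sponsor's. If it is not the cognitive scale, the 7.5-point difference and SD of 15 need to be justified for the scale chosen.
- If longitudinal methods are wanted, the wording can be moved to StimQ, which is the repeated measure.

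The cost is rewording sections 6.1 and 6.3 and aligning section 2.1 with the scale chosen. Site and demographics are already collected and no visit is added. The sample size stays at 100 unless the named scale calls for a different SD or difference.

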#### Study Interventions and Measures:

In this intervention, parent-infant dyads randomized to the digital arm will receive developmentally appropriate e-books. Those randomized to the standard arm will receive developmentally appropriate board books. Participants will receive either the e-book or board book for their 6, 9 and 12 month well visits. The developmentally appropriate books selected for each of the 3 well visits are as follows: [name] *Hop on Pop* for the 6 month well visit, Sandra Boynton's *Barnyard Dance* for the 9 month well visit, and Margaret Wise' *Goodnight Moon* for the 12 month well visit.

In addition to the books, parent-infant dyads in both arms will be provided information on the importance of early parent-child reading activity by pediatric clinicians using the Reach Out and Read framework.

We will collect standard measures of demographics (child age, sex, race/ethnicity, maternal age, family structure, maternal education level, and family income category), maternal adversity (9 ACE questions), maternal health literacy (SAHL), and maternal depressive symptoms (EPDS) at baseline. About 1 month after the infant has, or is age-eligible for, their 6 and 9 month well visits we will collect measures of reading activity (StimQ and ERPQ). Roughly 1 month after the infant has, or is age eligible for, their 12 month well visit, the infant will receive a developmental assessment (BSID-III), along with additional measures of reading activity (StimQ, ERPQ). They will additionally complete the paper-based DialogPR-I at this visit. A video recorded reading task will be obtained for up to 40 participants. These participants will be asked preliminary questions about their reading practices at home at the time of the video session.

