### **3.1.3 Screening Phase**

#### **3.1.3.1 Randomized Control Trial**

About 16% of the children seen at CHOP Primary Care Roxborough, 21% of those seen at CHOP Primary Care Indian Valley and 50% of those seen at CHOP Cobbs Creek have Medicaid. Children will be eligible to participate in this study if they were born  $\geq 35$  weeks estimated gestational age, without neurodevelopmental disabilities or congenital malformations, with Medicaid insurance (proxy measure for poverty), and at least 4 months of age at the time of enrollment. Children who are born premature  $< 35$  weeks EGA, who have neurodevelopmental disabilities, or who have congenital malformations are at increased risk of language delays and will be excluded. In addition, we will exclude families who do not speak English or Spanish, as the main measures of reading activity (StimQ, Appendix 5) and language development (Bayley Scales of Infant Development-III, Appendix 7) are only available in English and Spanish.

Potential subjects will be identified at the time of their four month well child visit using the electronic health record (EHR). The pediatrician or nurse overseeing the wellness visit will receive a notification to inquire whether the parent-child dyad would be interested in participating in the study. If the parent indicates interest, one of our research staff will be in contact to explain the study procedures, and arrange to meet with the parent-child dyad at a time before their 6 month wellness visit while the child is between 5 and 7 months of age. Research staff will obtain written informed consent from participants. Participants will be randomized to either the digital literacy arm or the standard literacy arm based on random assignment. Randomization sequences will be developed by the study team using computer-generated random numbers prior to study enrollment and will be placed in sealed opaque envelopes. Randomization will ensure equivalence between groups on measured and unmeasured characteristics and is considered to be the strongest protection against bias in study design.

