### **3.2 Allocation to Treatment Groups and Blinding**

Participants will be stratified by clinic site and randomized to receive literacy promotion using 1) standard early reader board books or 2) digital electronic early reader e-books. Randomization sequences will be developed by the study team using computer-generated random numbers prior

to study enrollment and will be placed in sealed opaque envelopes, assigning participants to one of the two treatment arms.

Participants in the video sub-study will also be randomized to determine the order in which they are asked to read the three versions of the selected book (print, basic e-book, enhanced e-book). As with the larger trial, randomization sequences will be developed by the study team using computer-generated random numbers prior to study enrollment and will be placed in sealed opaque envelopes, assigning participants to receive one of the six possible orders of the three book types.

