#### **3.3.2 Total Number of Study Sites/Total Number of Subjects Projected**

The randomized control trial will be conducted at three CHOP Care Network Practices: 1) Roxborough, located in Philadelphia, Pennsylvania, 2) Indian Valley located in Souderton, Pennsylvania and 3) Cobbs Creek, located in Philadelphia, Pennsylvania. These sites have been individually recruited to participate (see PeRC letter of support) and have agreed to participate.

Recruitment for the randomized control trial will stop when approximately 100 subjects (100 dyads of parent and infant) are enrolled. Recruitment for the video-taped component will stop when approximately 40 participants have completed the video and interview task.

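### Randomisation is stratified by clinic site, but section 6.3 names site in no analysis; adding it costs almost nothing and changes power by about -1 to +4 percentage points under assumed site effects

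*Combined protocol and SAP*

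**What the plan says.** **Design.** Section 3.2: "Participants will be stratified by clinic site and randomized to receive literacy promotion" in one of two arms. The Abstract (Study Design) and section 3.1.1 say the same. Section 3.3.2: "The randomized control trial will be conducted at three CHOP Care Network Practices", so there are three strata. On the sequence, section 3.2 says "Randomization sequences will be developed by the study team using computer-generated random numbers prior" to enrolment, with assignments held in sealed envelopes. No block scheme is described, and no number of dyads per site is given.

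**Analysis.** Section 6.3 is the only analysis text.
- BSID-III: regression models that "adjust for correlation in BSID-III scores over time and for potential confounding by demographic characteristics".
- Effect modification: similar models with arm interactions for ACE, SAHL and EPDS.
- Mediation: three regressions, written with arm, reading activity and language development only.
- StimQ: differences between "digital and standard groups at the 6, 9 and 12 month well visits will be assessed using t-tests".

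The Abstract (Study Interventions and Measures) lists the "standard measures of demographics (child age, sex, race/ethnicity, maternal age, family structure, maternal education level, and family income category". These are seven items, and clinic site is not one of them.

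**The concern.** When randomisation is restricted by a factor, the usual practice is to carry that factor into the analysis. Here the only factor used to stratify appears in none of the planned models. What happens next depends on how the sequence was built.

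- **Balanced within site (for example, blocked).** The arm estimate already benefits from the balance. A model without site leaves the between-site variation in the residual, so it reports a standard error larger than the true one.
- **Not balanced within site.** The unadjusted standard error is correct. If site predicts outcome, however, chance differences in site mix add variation that adjustment would remove.

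The trial is planned at a power of only 0.70, so a nearly free gain is worth having. Naming site in advance also settles a choice that section 6.3 leaves open, because it says only that regression models will be developed.

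**Working it through.** **Inputs from the documents.** Difference 7.5 points, alpha 0.05, power 0.70, 50 children per arm (section 6.3); SD 15 (Figure 1); three sites (section 3.3.2); one BSID-III assessment per child as the primary endpoint (section 6.1).

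**Assumed, because the documents give no value.** R², the share of BSID-III variance explained by site: 0, 0.02, 0.05 or 0.10. Site sizes 50, 26 and 24. No other covariates.

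**1. The plan's own figure.** n per arm = 2 × (1.960 + 0.524)² × 15² / 7.5² = 49.4, rounded up to 50, so 100 in total. This reproduces section 6.3 with a two-sided test. The other rows of Figure 1 (80 for 0.60, 90 for 0.65) reproduce as well. The standard error is 15 × √(2/50) = 3.00, and the power at 50 per arm is Φ(7.5/3.00 − 1.96) = 0.705.

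**2. Site added, normal approximation.** Residual SD = 15 × √(1 − R²).

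| R² | Residual SD | SE | Power | Total N for 0.70 |
|---|---|---|---|---|
| 0 | 15.00 | 3.00 | 0.705 | 100 |
| 0.02 | 14.85 | 2.97 | 0.714 | 98 |
| 0.05 | 14.62 | 2.92 | 0.727 | 94 |
| 0.10 | 14.23 | 2.85 | 0.750 | 90 |

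**3. Simulation.** 20,000 trials of 100 children per setting, two-sided 5%. A two-sample comparison is set against a linear model with arm and site. Changes are in percentage points, taken before rounding.

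| Allocation | R² | Type I error, without / with site | Power, without / with site | Change |
|---|---|---|---|---|
| Balanced within site | 0 | 0.050 / 0.049 | 0.697 / 0.698 | 0.0 |
| | 0.02 | 0.045 / 0.047 | 0.696 / 0.703 | +0.7 |
| | 0.05 | 0.044 / 0.050 | 0.705 / 0.720 | +1.6 |
| | 0.10 | 0.038 / 0.049 | 0.706 / 0.741 | +3.5 |
| Unblocked | 0 | 0.050 / 0.051 | 0.694 / 0.684 | −1.0 |
| | 0.02 | 0.050 / 0.050 | 0.694 / 0.695 | 0.0 |
| | 0.05 | 0.050 / 0.050 | 0.694 / 0.708 | +1.4 |
| | 0.10 | 0.050 / 0.049 | 0.690 / 0.729 | +3.9 |

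**4. Why the balanced case is conservative.** With balance, the two estimates are identical and vary equally; only the reported standard error differs. At R² = 0.05 the true standard error is 2.92 and the unadjusted model reports 2.99. At R² = 0.10 the figures are 2.83 and 2.99. The expected type I error is 2Φ(−1.96/√(1 − R²)). This gives 2Φ(−2.011) = 0.044 and 2Φ(−2.066) = 0.039, in line with the simulated 0.044 and 0.038.

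**5. What R² = 0.10 would require.** If half the children came from one clinic and that clinic differed from the rest by a gap g, then R² = 0.25 × g²/225, so g = √(900 × R²). R² of 0.02, 0.05 and 0.10 correspond to gaps of about 4.2, 6.7 and 9.5 points. The top of the range therefore needs a between-clinic gap larger than the 7.5 points the plan calls clinically significant.

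**6. A second set of assumptions.** Take sites in the ratio 16:21:50 (which supposes equal clinic sizes) and Cobbs Creek 5, 8 or 10 points below the other two. Site then explains p(1 − p)g²/225 with p = 50/87, that is 2.7%, 7.0% or 10.9%. Simulated power goes from 0.70, 0.70 and 0.71 to 0.71, 0.72 and 0.74 with balance, and from 0.70, 0.69 and 0.69 to 0.70, 0.71 and 0.73 without. The range is the same as in step 3.

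**The case against.** The strongest reply has four parts.

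**The loss is not established.** A reader might infer that the between-arm standard errors are necessarily wrong and that precision is certainly lost. The documents do not support that. No section says that allocation is balanced within site, and without balance the unadjusted standard error is valid. With balance, the estimator itself loses no precision. In neither case is there a false-positive risk: the error, where it exists, widens intervals. Nor is chance site imbalance a bias, since the valid standard error already reflects it. This part stands.

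**The documents do not show that participants differ by site.** Section 3.1.3.1 says "About 16% of the children seen at CHOP Primary Care Roxborough, 21% of those seen at CHOP Primary Care Indian Valley" and half of those at Cobbs Creek have Medicaid, and a reader might take this as evidence of different patient mix in the trial. Those shares describe everyone seen at each clinic. Section 3.4.1.1 requires Medicaid for every enrolled child, so the shares say nothing about BSID-III differences among participants. This part stands too.

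**Site is unspecified in the BSID-III models, not excluded.** The covariate list is open, and the Abstract lists what will be collected, not what will be modelled. Race/ethnicity, maternal education and income may carry much of any site difference, and the calculations above do not include them. This stands for the main and interaction models. It does not help the StimQ t-tests, which take no covariates, or the mediation models, which name none. Clinicians at each practice also give the books and the reading guidance (sections 3.1.4 and 4.2), so a site effect beyond family demographics is possible, though the documents do not show one.

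**Some endpoints have no stated method.** Section 6.3 gives none for DialogPR-I or the ERPQ, so it cannot be said that their analysis omits site. That is a separate gap.

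**Conclusion.** The omission is real: the stratification factor appears in no analysis that section 6.3 describes. Its consequence is conditional and small. Over an assumed R² of 0 to 0.10, adding site changes power by between about −1 and +4 percentage points. The loss arises only when site explains nothing and allocation is unblocked (0.694 to 0.684). The largest gain needs R² of about 0.10 with no demographic adjustment. The effect on the planned demographics-adjusted BSID-III model has not been computed and should be smaller wherever those covariates track site. No size was computed for StimQ.

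This is a low-cost improvement to the plan. It is not a threat to the trial's validity, and it does not show that the primary analysis would be wrong.

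**What to change.** In section 6.3:

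1. State that the BSID-III models (main, interaction and each of the mediation regressions) include clinic site as a fixed effect with two indicator terms, in addition to the demographic covariates.
2. Replace the StimQ t-tests with linear models containing arm and site.

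Saying in section 3.2 whether the sequence is balanced within site would show which of the two cases applies, but the change is sensible either way.

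**Cost.** A sentence or two of text and two degrees of freedom per model. No new data collection should be needed, since site must be known to randomise. If site turns out to be unrelated to outcome and allocation is unblocked, the price is about 1 percentage point of power.
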